1. LAY SUMMARY

Medial osteoarthritis – wearing of the inside of the knee joint – can be treated with either knee replacement or osteotomy procedures. With the former, either part or the whole of the knee joint is replaced. With the latter, it involves cutting the tibial and or femoral bone and introducing an opening wedge to change the angle of the knee joint and thereby shift the patient's weight from the medial to the lateral side (outside) of the knee. For all major knee operations, post-surgery the site of operation can be painful. Increased pain may limit a patient's progress with post-operative mobilisation. Therefore, research is already ongoing in the field of knee surgery to determine if different type of bandaging of the affected leg post-surgery may improve patient and clinical outcomes. A new method is now available which involves bandaging that compresses the leg. This may reduce pain. This present study aims to assess if compression bandaging is better than standard non-compression bandaging in terms of keeping a patient comfortable by reducing pain and possibly improving other clinical outcomes too. A total of 148 patients will be recruited and allocated to either standard bandaging (74 patients) or Andoflex TLC Calamine Lite compression bandaging (also 74 patients); follow-up of patients will be up to 12 weeks post-surgery. Apart from clinical outcomes such as the degree and type of pain experienced by patients, safety data such as incidence of infection and deep vein thrombosis/pulmonary embolism, plus readmission to hospital will be recorded too. The main objective of the study is whether Andoflex TLC Calamine Lite compression bandaging (worn for 5 days post-surgery) is significantly better than standard bandaging (worn for up to 48 hours post-surgery) at day 5 post-surgery when measured on a visual display pain scale.

2. INTRODUCTION

Major knee surgery is associated with post-surgery pain. The surgical site is subject to bleeding and inflammation-related fluid build-up in the intraarticular tissues (Holm et al, 2020). Pain may impact negatively on recovery time and active early rehabilitation due to physical impairment that it may cause ((Mizner & Snyder-Mackler, 2005). This in turn may increase hospital length of stay and poor patient reported-outcomes (Moretti et al, 2012; Williams et al, 2013). Many service improvement programmes and techniques have been introduced in knee surgery over the years, including means to reduce intra-articular bleeding, tourniquets and medication (Martin et al , 2014). Initiatives in post-surgical management of patients have been less successful. These include methods such as the use of a cold compress (Morsi 2002), cryotherapy (Adie et al, 2012), elastic bandaging (Hughes et al, 1995) and some types of compression bandaging (Anderson et al, 2008; Charalambides et al, 2005).

Compression bandage therapy is established treatment of venous ulcers and lymphoedema (Franks et al, 2004, Pike 2011). It is hypothesised that the application of this external compression aids venous return and reduces hydrostatic pressure in the leg by (i) improving the efficacy of the calf muscle pump and (ii) moving blood from the superficial to deep venous system, subsequently allowing movement of fluid from the interstitial space. The use of inelastic bandages are preferred in arthroplasty as they have a low, tolerable resting pressure but a more effective activation of the deep venous system and calf muscle pump with ambulation compared to their elastic counterparts (Spence & Cahall, 1996).

The efficacy in total knee arthroplasty is still unclear due to conflicting results in the literature and heterogeneous methodology (Munk et al, 2013; Pinsornsak P & Chumchuen, 2013; Cheung et al, 2014). An acute pain study by Andersen et al (2008) utilised a compression bandage consisting of a double layer of soft padding and an outer elastic adhesive dressing compared with standard bandage in a randomised controlled trial of 48 patients. The intervention group had significantly reduced pain at 8 hours compared to a control group, though the bandage was combined with local anaesthetic infiltration.

Direct evidence on the role that different bandaging may play in improving post-operative outcomes after high tibial, distal femoral or double osteotomy is limited. Most osteotomy studies focus heavily on post-operative accuracy achieved in correcting the knee joint angle at circa 6 months post-surgery onwards (Amendola & Bonasia, 2010; Khoshbin et al, 2017). Other surgery-related findings have been reported as an incidental finding, such as 2 DVTs in a sample of 47 HTO patients by Miller et al (2009). In a recent study involving osteotomy patients, we showed a marked change in the type and temporal profile of pain experienced by patients post-surgery, see Table 1 (Jonker et al, 2020).

Table 1, At rest pain level related to affected leg post-surgery, measured using 10-cm visual display scale (Jonker et al, 2020)

Time point	Standard care arm (n = 18)	Coban™ 2 arm (n = 18)	p-value
5 days post-surgery, median (IQR)	5.5 (2.5-7.0)	2.5 (1.5-6.5)	0.068
12 days post-surgery, median (IQR)	4.0 (3.0-5.3)	2.3 (1.4-5.6)	0.39
6 weeks post-surgery, value (IQR)	2.0 (1.5-2.5)#	2.8 (1.0-5.8)*	0.21

[#]n = 16; * n=17

Taken together, preliminary data suggests that the use of an inelastic, short-stretch 2-layer compression bandage following knee surgery is a safe technique that may improve health outcomes. Therefore, we aim to assess its effectiveness and safety in a knee surgery patient population and we will focus on outcome measures up to 12 weeks post-surgery.

3. INVESTIGATIONAL DEVICE & INTERVENTION

3.1 Intervention

3.1.1 Standard care (control) arm

As soon as the operation is finished and a wound dressing has been applied, the standard bandaging is applied. One layer of soft synthetic bandage, stretching from proximal tibia to distal femur covered by a further layer of crepe bandage prior to or after tourniquet deflation, with 50% overlap of each layer (cryotherapy can be applied over this if standard of care). The bandaging will be removed approximately 48 hours post-operatively whilst leaving the dressing in situ. The bandages can be removed sooner than 48 hours if the patients find them very uncomfortable, or in the event of any adverse events that would require their removal, or if a cryocuff is applied post-operatively.

3.1.2 Andoflex TLC Calamine Lite compression bandaging (intervention) arm

As with standard bandaging, the Andoflex TLC Calamine Lite compression bandage will be applied over the routine surgical wound dressing. A foam inner bandage (Andoflex TLC Calamine Lite 2, Milliken Healthcare) is applied from the toe to the groin on the affected leg with minimal overlap. The second layer, which is the actual compression bandage (Andoflex TLC Calamine Lite 2, Milliken Healthcare) is applied at full stretch and with a 50% overlap of bandage to ensure adequate

compression in the application. The mode of action of this two layer compressive bandage kit is of particular practical use, since it is tolerable for patients overnight due to its low resting pressure. Furthermore, it produces high pressure compression with movement to stimulate the calf muscle pump. The bandage is applied from the toes upwards. The application of bandage from thigh to groin requires removal of the tourniquet first and so the leg is kept elevated until the bandaging is complete. There is a training video available on correct application of the bandages: https://www.youtube.com/watch?v=pal0pY_cTRc (Andoflex is known as Coflex in some other countries such as the USA).

The compression bandage has been shown to effect compression for up to a week. To balance compression and comfort, patients are asked to continue wearing the bandage for 5 consecutive days after surgery. The bandages can be removed sooner if the patients find them very uncomfortable (which will be classed as an adverse event) or in the event of any other adverse events that would require their removal – this will be recorded on the Case Report Form and in medical notes. If requested by the patient, they are allowed to return to a hospital clinic to have the Andoflex TLC Calamine Lite bandaging reapplied if for any reason the first set needed to be taken off. To maintain consistency, clinical healthcare professionals who apply a new Andoflex TLC Calamine Lite bandage need to sign a declaration that they have watched the training video and are comfortable complying with the instructions. Full product information on the Andoflex TLC Calamine 2-layer compression system can be found on the Andover Healthcare Inc website https://andoverhealthcare.com/product/coflex-tlc-calamine/

There are two pressure options: compression of either (standard compression) 35-40 mmHg or ('Lite' compression) 25-30 mmHg, for patients with an ABPI of ≥ 0.8 or ≥ 0.5 respectively. Layer 1 is a soft foam roll impregnated with calamine that is designed to soothe and calm skin with multiple wounds or other skin conditions. Layer 2 is a non-latex short stretch compression bandage that sticks to itself and features Easy HandTear Technology, eliminating the need for scissors. Absorbs 20xs its dry weight vs. traditional Unna Boot, and 50% more active ingredients than traditional Unna Boot. It provides a two-step short stretch performance with high working pressure and low resting pressure. Visual indicators are provided for ease of application - ovals become circles when the intended compression is achieved.

Apart from the difference in type of bandage, the protocol for the Andoflex TLC Calamine Lite arm is identical to that of the standard care group (cryocuff can be applied to this treatment arm, but will be applied over the bandaging). Used bandaging will be disposed of in line with local guidelines on disposal of clinical waste if in clinical location, or by patient in home setting.

Figures 1 & 2. Standard wool and crepe bandaging (top) vs Andoflex TLC Calamine Lite dual layer compression bandaging (bottom)

4. STUDY HYPOTHESIS

4.1 **Primary objective**

 To assess the efficacy of Andoflex TLC Calamine Lite compression bandaging for reduction of post-operative pain after knee surgery compared with standard care bandaging.

4.2 Secondary objective

- To assess the type of pain experienced by patients wearing either Andoflex TLC Calamine Lite compression bandaging or crepe bandaging.
- To assess the efficacy of Andoflex TLC Calamine Lite compression bandaging for improvement of post-operative patient-reported outcome measures, including knee functionality, after knee surgery when compared with standard care bandaging.
- To determine if there is a difference in pain outcomes dependent on the knee surgery subcohort (knee replacement, osteotomy).

5. STUDY PROTOCOL

5.1 Study design, recruitment sites and timeline

This concerns a multi-centre, controlled prospective randomized study of CE-marked medical devices. The study will be carried out in the following NHS Trust:

- North Cumbria Integrated Care NHS Foundation Trust (both Cumberland Infirmary, Carlisle, and West Cumberland Hospital, Whitehaven. Cl [name])

The study will take place in a hospital setting with support and oversight from the treating orthopaedic surgeon, nursing staff and research staff. Where appropriate, research delivery staff will be delegated to provide support with data collection and processing.

Table 2. Anticipated timeline

Month	Setup	Recruitment	Analysis	Finalise
May 2021	Submission for NRES/ HRA approval			
Jun 2021	NIHR portfolio adoption			
Jun 2021	NRES/HRA and Trust approval			
Jul 2021		Start recruitment		
Jul 2022		Finish recruitment		
Oct 2022			Follow-up complete; Analyse data.	
Nov 2022				manuscript & report writing

5.2 Participant identification and research setting

Participants will be recruited from orthopaedics clinics and all eligible patients will be invited to take part until the required numbers have been achieved. Identification will be by the orthopaedics clinical team, who are supporting the study. A screening form will be completed for potentially eligible patients to confirm that they indeed meet the trial criteria.

To summarise, the orthopaedic team will:

- Identify potentially eligible patients and ask verbal consent for them being approached about the study by a member of the R&D team
- Complete the incl/excl criteria part of the screening form (if a patient has given verbal consent to being approached by the research team then they can complete the screening form)

5.3 Consent and recruitment

Those eligible will be approached and provided with an information pack and consent form, which will be signed to indicate that informed consent has been given. Patients will be given ample time to

consider taking part, more than 24 hours if they wish. The study will be first mentioned at an orthopaedics out-patient clinic visit. The direct healthcare professional will first approach a patient about the study, and after verbal consent by the patient the healthcare professional themselves or a member of the research team can go through the informed consent process.

Patients are also allowed to consent to taking part when first approached as long as the study has been discussed with the patient and they have been given time to read the patient information leaflet and opportunity to ask any questions that they may have. Participants will receive no incentives and consent will be regarded as a process and not a one-off event. Participants are free to withdraw from the study at any time without the need to give any reasons for withdrawal. Their standard of care will not be affected by either declining to participate in the study or withdrawing during participation. Data collected up to the date of withdrawal will be retained for analysis.

Participants will be randomised to either the control bandage group (TaU) or the intervention group (Andoflex TLC Calamine Lite) any time up until the day of surgery.

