5.4 Follow-up

Patients are in the study for a period of 12 weeks. Thereafter, the patient will be followed up as they would be in normal clinical practice. Study visits are aligned to hospital/clinic visits where possible. Baseline data can be collected on the day of surgery (prior the actual operation), and 12 day and 12 week post-surgery data can be collected when the patient attends for standard follow-up in the orthopaedics out-patient department. The data at day 3, 5, day 12 and week 3 falls outside these dates. For all outcome measures, data can be collected over the phone, via e-mail or by mail (whichever is preferred by the patient – mail is by use of freepost, to avoid patients incurring any costs). The researcher can also send reminders to the participant regarding the completion of certain outcome data at the aforementioned follow-up time points.

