5.5 Outcome measures

5.5.1 **Primary outcome measures**

To determine the level of operation-site related pain experienced at day 5 post-operation and to compare the average pain scores of patients in the control and Andoflex TLC Calamine Lite arm respectively, through administration of 10 cm visual descriptor scale (VDS) for pain.

The study is powered to detect the established minimal clinically important difference (MCID) of 1.5 cm on a 10 cm VDS pain.

5.5.2 **Secondary outcome measures**

All the outcome measures are summarised in Table 3.

Table 3. Overview of measurements

Weeks	-12 weeks to day of surgery	0 surgery	3 days ^{##}	5 days ^{##}	12 days [#]	6 weeks*	12 weeks *
Application bandage		Х					
straight after surgery							
VDS pain scale (at rest)	Χ		Χ	Χ	Χ	Χ	
VDS pain scale (walking)	Х		Χ	Χ	Χ	X	
McGill pain	Х		Χ	Χ	Χ	X	
questionnaire							
Limb range of motion	Х					X	
KOOS score	Х					X	Χ
Patient satisfaction					Χ	(X, if not	
questionnaire re						returned	
bandaging						yet at 12	
						days)	

^{*} Allowed to be up to 2 weeks early or late # Allowed to be up to 3 days early or late ## Allowed to be up to 1 day early or late

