6.1.1 Randomisation

Following written consent, participants are allocated at random to the control or Andoflex TLC Calamine Lite intervention group, using a randomised sequence from the freeware randomisation programme, see https://www.randomizer.org/. No stratified or block randomisation will be undertaken, apart randomisation per surgery type.

Sequential envelopes with each next randomisation allocation will be used to achieve concealment and these will be kept in the research department. The researcher or regular healthcare professional for the participant in question can e-mail ([contact]) or phone the R&D Dept ([name]) to determine which treatment the next participant has been allocated to.

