8.2 Primary outcome statistics

To determine the level of operation-site related pain experienced at day 5 post-operation and to compare the average pain scores of patients in the control and Andoflex TLC Calamine Lite arm respectively, through administration of 10 cm visual descriptor scale (VDS) for pain.

Confidential – This document and the information contained herein may not be reproduced, used or disclosed without written permission from North Cumbria Integrated Care NHS Foundation Trust Page | 18

The study is powered to detect the established minimal clinically important difference (MCID) of 1.5 cm on a 10 cm VDS pain.

The average difference between time points will be calculated per group, 5 days post-surgery weeks being the primary endpoint. Three days, 12 days and 6 weeks post-surgery will also be analysed. To compare the groups, the Mann-Whitney U-test will be applied.

To avoid relying on one outcome measure related to pain, at 3, 5, 12 days, and 6 weeks post-surgery pain perception will also be measured using the short form McGill pain questionnaire. Again, to compare groups the Mann-Whitney U-test will be applied.

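### The readable protocol lets the allocation be obtained before baseline pain, McGill and KOOS are completed; this threatens baseline-referenced analyses, and the primary comparison only if it is a change from baseline.

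*Protocol*

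**What the plan says.** **Allocation.** Section 6.1.1 places randomisation after consent: "Following written consent, participants are allocated at random to the control or Andoflex TLC Calamine Lite intervention group". Section 5.3 sets no earliest date beyond that ("Patients are also allowed to consent to taking part when first approached") and lets randomisation happen "any time up until the day of surgery". Under section 6.1.1 the researcher or the patient's usual healthcare professional contacts the R&D department "to determine which treatment the next participant has been allocated to". Nothing there restricts when the call may be made or whether the patient may be told.

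**Baseline.** Section 5.4 states "Baseline data can be collected on the day of surgery (prior the actual operation". The baseline column of Table 3 runs from minus "12 weeks to day of surgery". It covers VDS at rest and walking, McGill, range of motion and KOOS.

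**Use of baseline.** Section 5.5.1 gives the primary outcome as a day-5 comparison: "To determine the level of operation-site related pain experienced at day 5 post-operation and to compare the average pain scores of patients". Section 8.2 opens the same way, then adds: "The average difference between time points will be calculated per group". It does not say which time point is subtracted. The protocol summary calls the pre-surgery KOOS and range-of-motion measurements the baseline, and section 8.3 applies the outcome statistics to both measures before surgery and at 12 weeks.

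**The concern.** VDS, McGill and KOOS are self-reported. A patient who already knows which bandage is coming may rate the knee differently from one who does not, out of hope, disappointment or a wish to justify the choice. Randomisation makes the arms comparable at baseline only for values that the allocation cannot have influenced. Once the arm is known, the baseline is in effect a post-randomisation measurement.

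The two bandages look different and cover different lengths of leg (sections 3.1.1 and 3.1.2), so post-operative self-report can hardly be masked. Baseline can be protected, simply by taking it first.

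Two things are at stake. One is the validity of any analysis that uses baseline as a reference, and of the baseline comparison itself. The other is loss after allocation: the earlier the arm is known, the longer the period before surgery in which a patient can cancel or withdraw because of it. Such a patient has no day-5 score.

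**Working it through.** **Step 1. Is the unwanted order permitted?** Take a patient who consents at the first clinic approach (allowed by 5.3). A staff member then asks R&D for the allocation (allowed by 6.1.1, at any time under 5.3), the patient learns the arm, and the baseline forms are filled in on the morning of surgery (allowed by 5.4 and Table 3). Every step complies with the readable text. The protocol does not give the gap between consent and surgery. That it may be weeks is inferred from clinic consent and the 12-week baseline window.

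**Step 2. Does baseline enter the primary comparison?**

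- *Day-5 score.* The primary objective in the summary, section 5.5.1, section 6.1 and the opening of section 8.2 all describe day-5 pain compared between arms. Table 4 is built on day-5 means of 5.0 and 3.5.
- *Change from baseline.* Only the sentence in section 8.2 on differences between time points points this way. Day 3 is also to be analysed, and the only VDS before day 3 in Table 3 is baseline, so a difference ending at day 3 would naturally start from baseline. But the sentence names no reference, describes a per-group calculation, and is separate from the sentence that names the Mann-Whitney test.

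The balance favours the day-5 score, but section 8.2 leaves room for the other reading.

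**Step 3. The plan's own figure.** Table 4 gives 62 per surgery type before drop-out. With d = 1.5/2 = 0.75, two-sided 5%, noncentral t and Mann-Whitney efficiency 3/π, 30 per arm gives power 0.796 and 31 per arm gives 0.810. So 31 per arm, 62 in total, is reproduced. Pooling both surgery types gives 2 × 31 = 62 per arm. Fixing the order of baseline and allocation does not change these numbers.

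**Step 4. Size, on the change-score reading only.** The SD of 2 cm is from Table 4, where it belongs to the day-5 score. Assumptions not in the protocol: baseline SD also 2 cm, baseline to day-5 correlation r of 0.3 to 0.5, no true effect, and a between-arm shift b in mean baseline caused by knowing the arm.

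- SD of change = 2 × √(2(1 − r)): 2.00 at r = 0.5, 2.37 at r = 0.3.
- SE = SD of change × √(2/(n × 3/π)).
- False-positive rate = 1 − Φ(1.96 − b/SE) + Φ(−1.96 − b/SE).

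| n per arm | r | b (cm) | SE | b/SE | False-positive rate |
|---|---|---|---|---|---|
| 62 | 0.5 | 0.3 | 0.368 | 0.82 | 12.9% |
| 62 | 0.5 | 0.5 | 0.368 | 1.36 | 27.5% |
| 31 | 0.3 | 0.5 | 0.615 | 0.81 | 12.8% |
| 31 | 0.5 | 0.5 | 0.520 | 0.96 | 16.1% |

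With the t distribution in place of the normal, the first two rows become 12.8% and 27.1%.

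A change score carries the whole of b. An analysis adjusted for baseline would carry r × b, for example 0.3 × 0.5 = 0.15 cm or 0.5 × 0.5 = 0.25 cm. A comparison of day-5 scores alone carries none of it.

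**The case against.** The strongest reply is that the primary outcome is a day-5 score, stated several times and built into the sample size, so a disturbed baseline cannot reach it. That largely stands. A reader might infer from section 8.2 that baseline is part of the primary comparison and that its false-positive rate is therefore inflated. The protocol does not support that as a statement of fact: one sentence is ambiguous and the other definitions point the other way.

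Further objections, and what remains of each:

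- *Unseen flowcharts.* Appendices 2 and 3 appear as headings only. The participant flowchart may show baseline before randomisation. The point is therefore limited to the readable text, which would still need to agree with the figure.
- *Disclosure to patients is inferred.* Section 6.1.1 has staff, not patients, asking for the allocation. That is correct: early disclosure is permitted, not prescribed. But nothing withholds the arm either.
- *The mechanism is modest.* The VDS item asks about pain over the last day, before any bandage is applied, and the direction of a shift cannot be predicted. Both are true. The shift is assumed, and its real size may be close to nil.
- *Cancellations are covered.* Section 6.1 plans intention-to-treat analysis and allows 20% attrition. The allowance protects numbers, but not against loss that differs by arm. The protocol contains no evidence that such loss will occur. Its statements on data from withdrawn patients also conflict (retained in 5.3, excluded in 6.3), which makes avoidable loss after allocation less welcome.

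**Conclusion.** The point holds in a limited form. The readable text allows the arm to be known before the self-reported baseline is completed, and it describes no blinding. Baseline values, and any analysis of KOOS, range of motion or McGill that refers to them, can be affected. The opportunity to cancel or withdraw knowing the arm is also longer than it needs to be.

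For the primary comparison the effect is conditional. If it is the day-5 score, the added bias is zero. If it is a change from baseline, an assumed shift of 0.3 to 0.5 cm (20% to 33% of the 1.5 cm target difference) would raise the false-positive rate from 5% to about 13% to 27% at 62 per arm with r = 0.5. At 31 per arm, a 0.5 cm shift would raise it to about 13% to 16% for r of 0.3 to 0.5. These figures illustrate sensitivity and do not estimate what will happen: the shift, the baseline SD and the correlation are not in the protocol. The change is worth making because it costs almost nothing.

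**What to change.** - **Sections 5.3 and 6.1.1:** fix one order. Written consent comes first, then all baseline measures (VDS at rest and walking, McGill, KOOS, range of motion), then release of the next allocation by R&D, as close to surgery as practicable. R&D should confirm that baseline is complete before opening the envelope.
- **Log:** record the time of baseline completion and the time of allocation release for each participant, so that the order can be shown.
- **Section 8.2:** state that the primary comparison is the day-5 at-rest VDS score between arms, and say what the difference between time points refers to.
- **Appendix 2:** check that the flowchart shows the same order.

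The cost is protocol wording and one log entry per participant, with no change in sample size. The practical downside is that both bandage types must be available in theatre, because the allocation is known late.
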